7.2 Randomization, blinding and treatment allocation

Potential participants are randomly allocated to the experimental or control group before the start of the study, i.e. before inclusion. In this way, the potential participants allocated to the control group can receive other information about this study than potential participants allocated to the experimental group. This is done to prevent occurrence of the bias that might be present when the patients in the control group are aware of the working mechanism of motor imagery, and its potential benefits. When the patients in the control group know that they participate in a study that is conducted to determine whether motor imagery can promote the recovery after DRF, it is possible that they perform motor imagery during the immobilization, or pay more attention to their injured hand as normal. Such bias cannot be detected and may severely confound the results of this study. Therefore, we decided to keep the patients in the control group ignorant.

Because randomization is performed before inclusion, it is likely that some patients will decide not to participate, reducing the number of participants in that group. The experience of 2.5 years inclusion teaches us that the response rate to participate is different for each group (experimental group 35%, control group 62%). Therefore, the number of patients who will be asked to participate is controlled for this difference. This means that more patients are allocated to the experimental group, than to the control group. The random allocation is performed with remaining equal group sizes, and equal distribution of the different fracture types (intra-articular vs. extra-articular distal radius fractures).

The randomization process is done using PASW Statistics 18. Subject numbers are randomly allocated to the experimental or the control group. The order in which the patients receive their initial treatment determines their subject number. There is no blinding of the patients, nor the researcher is blinded.

Based on national statistics concerning the diseases and injuries diagnosed on a yearly basis, it is expected that 6-7 DRF-patients will be treated in the UMCG every week, and 2-3 of them will be women of 45-75 years of age (58).

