Sponsor	The sponsor is the party that commissions the organisation or performance of the research, for example a pharmaceutical company, academic hospital, scientific organisation or investigator. A party that provides funding for a study but does not commission it is not regarded as the sponsor, but referred to as a subsidising party.
SUSAR	Suspected Unexpected Serious Adverse Reaction
Wbp	Personal Data Protection Act (in Dutch: Wet Bescherming Persoonsgegevens)
WMO	Medical Research Involving Human Subjects Act (in Dutch: Wet Medisch-wetenschappelijk Onderzoek met Mensen)

SUMMARY

Rationale: Distal radius fracture (DRF) is a common injury that may lead to prolonged function restrictions, decreased range of motion, reduced grip strength and pain. These symptoms may be caused by physical changes due to the injury and/or by the 4-6 weeks immobilization that is part of the conservative treatment. However, it might also be that neural changes during the immobilization play an important role. Such changes might be prevented by motor imagery training during the immobilization period. So, when neural changes are prevented, this may lead to a better functional outcome.

Objective: The objective is to improve the functional outcome in distal radius fracture patients, specified as an increase in function, dexterity, grip strength, range of motion, and decrease of pain.

Study design: Parallel group randomized controlled trial, with a post-test only control group design. Patients in the experimental group perform motor imagery training during the immobilization period, in addition to the regular treatment. Patients in the control group receive regular treatment.

Study population: Female DRF-patients who are conservatively treated by a cast, aged 45-75 years. The fracture must be a low energy trauma caused by a fall. Patients with a score higher than 72 on the internal scale of the Vividness of Motor Imagery Questionnaire (VMIQ) are excluded, as well as patients with co-morbidities that might influence the wrist function, or motor imagery-ability, and patients with no understanding of Dutch language.

The patients are randomly allocated to the experimental or control group by restricted randomization to ensure equal group sizes. The randomization is conducted with use of PASW Statistics 18.

Intervention: Motor imagery training; 4 times a day 7 minutes of motor imagery training for 3 weeks (depending on duration of immobilization period).

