9. STATISTICAL ANALYSIS

9.1 *Descriptive statistics*

Patient characteristics are presented using descriptive statistics for the potential confounding variables.

Data of the main outcome measure are of interval level of measurement. The ROM and grip strength are of ratio level of measurement. Hence, the descriptive statistics of these outcome measures are presented by the mean and standard deviation. Dexterity is measured using the SODA, and the data of this instrument are of ordinal level of measurement. Therefore, the descriptive statistics are presented by the median and range. Pain is measured using the VAS, which provides data of interval level of measurement. So, the descriptive statistics are presented by the mean and standard deviation.

9.2 *Univariate analysis*

The effectiveness of motor imagery training will be determined with use of a multivariate analysis for the parametric data (as described later in chapter 9.3). The non-parametric data are analyzed using a Mann-Whitney U test for each variable, to determine whether the groups are different. This test is also used when the data is not normally distributed.

9.3 *Multivariate analysis*

With use of a MANOVA, the difference between the experimental and control group will be determined for each measurement time and for each variable. There are two factors included in the analysis; a between factor 'group' and a within factor 'time'. The hypothesis is tested using two-tailed tests, with a significance level of 5%. The data of the patients in both groups will be analyzed using an intention to treat analysis.

9.4 *Interim analysis (if applicable)*

An interim analysis will be conducted to determine the effect of motor imagery training on hand function, dexterity, ROM, grip strength and pain. When the results of this analysis shows serious unwanted effects of motor imagery training, this study will be terminated.

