10.2 Recruitment and consent

The diagnose list of the Emergency department of the University Medical Center Groningen is checked daily for DRF. Within 48 hours after initial treatment, an information letter is sent to the patients who reach the inclusion criteria to inform them about this study and ask them for their participation. As explained in chapter 7.2, potential participants are already allocated to the experimental or control group, so the patients in the experimental group receive an information letter that is different from the information letter that the patients in the control group receive. In this letter, the patients are asked for their participation. When they are willing to participate, the patients return a signed informed consent. One week after initial treatment, the patients return to the hospital for a check-up appointment. At that moment, they have had 5-7 days to consider their participation. In the outpatient clinic, the patients who sent back a signed informed consent are asked to fill out the Vividness of Motor Imagery Questionnaire (VMIQ). The outcome of this test determines the final inclusion or exclusion of the patient. Patients who have an internal VMIQ-score > 72 are excluded, because this indicates that their ability to perform motor imagery is low. The patients with a VMIQ-score ≤ 72 are included. Patients allocated to the control group receive information about the measurements, the measurement times and the duration of the study. Patients allocated to the experimental group receive the same information about the measurements and duration, but also instructions to do motor imagery training. The patients in both groups will receive an information letter, but the patients in the experimental group also receive a letter that contains the instructions to do motor imagery training.

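### Acceptance of 35% versus 62% after arm-specific letters leaves two differently self-selected groups; inviting more experimental patients evens out the numbers only, and the intention-to-treat label does not cover those who decline

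*Combined protocol and SAP*

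**What the plan says.** Section 7.2 states: "Potential participants are randomly allocated to the experimental or control group before the start of the study, i.e. before inclusion". The reason given is to keep controls unaware of motor imagery, so that they do not practise it themselves or attend more to the injured hand. Section 10.2 confirms that "the patients in the experimental group receive an information letter that is different from the information letter that the patients in the control group receive", and that these letters come before consent.

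After 2.5 years of recruitment, 7.2 reports that "the response rate to participate is different for each group (experimental group 35%, control group 62"%). The response is: "Therefore, the number of patients who will be asked to participate is controlled for this difference". It adds: "This means that more patients are allocated to the experimental group, than to the control group". The aim is also stated: "The random allocation is performed with remaining equal group sizes, and equal distribution of the different fracture types".

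The Summary describes a "Parallel group randomized controlled trial, with a post-test only control group design". Section 3 places the first outcome measurement at cast removal, after the training period. Section 7.1.3 lists six confounders to be used as covariates: age, motor imagery ability, fracture type, occupation, sport and use of the casted hand. Section 9.3 names two factors only, group and time, and compares the groups at each measurement time and for each variable. It says: "The data of the patients in both groups will be analyzed using an intention to treat analysis".

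**The concern.** Randomisation makes the allocated groups comparable. It does not make comparable the subsets that choose to take part when that choice follows information that differs by arm. The plan's own acceptance rates show that the choice does depend on arm. Section 7.2 treats this as a shortfall in numbers, but inviting more people at the same 35% leaves the accepters the same kind of patient.

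The primary outcome is self-rated and nobody is blinded, so willingness to take part, early pain and early function could plausibly relate to the PRWHE. No outcome is measured before training, so the groups cannot be compared on early function or pain, nor adjusted for it. At stake is how far a difference between the groups, or the absence of one, can be read as the effect of the training.

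**Working it through.** **Inputs.** Total sample 52, SD 26.13 and difference 5.3 PRWHE points (4.4); acceptance 35% and 62% (7.2); equal groups (7.2), hence 52/2 = 26 per arm.

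**1. The plan's own figure.** 5.3/26.13 = 0.203, the stated effect size of 0.20. A repeated-measures within-between interaction with f = 0.20, two groups, two measurements, alpha 5%, and an assumed default correlation of 0.5 gives 80.7% power at N = 52. So 52 reproduces, and this point does not turn on it.

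**2. What topping up does.**
- Experimental: 26/0.35 = 74.3, so 75 invitations and 75 − 26 = 49 decliners.
- Control: 26/0.62 = 41.9, so 42 invitations and 42 − 26 = 16 decliners.
- Ratio of invitations: 0.62/0.35 = 1.77.

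These counts cover consent only; VMIQ exclusions would raise them. Under 9.3 the 49 and 16 are allocated but not analysed.

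**3. Could the acceptance gap be chance?** The denominators are not given. If each arm had 25, 50, 100 or 150 invitations (assumption), Fisher's exact test gives p = 0.09, 0.016, 0.0002 or below 0.0001.

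**4. Illustration of size.** Assume one normal willingness scale with perfect threshold selection in both arms. The mean willingness of the accepting fraction p is φ(c)/p, with c = Φ⁻¹(1 − p).
- p = 0.35: 1.058 SD.
- p = 0.62: 0.614 SD.
- Gap: 1.058 − 0.614 = 0.444 SD, and 0.444 × 26.13 = 11.6 points.

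Multiply by an assumed correlation r between willingness and PRWHE. The last column is the true type I error of a two-group t test at one visit, 26 per arm, nominal 5%.

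| r | Difference in level with no treatment effect | Type I error |
|---|---|---|
| 0.1 | 1.2 points | 5.3% |
| 0.2 | 2.3 points | 6.1% |
| 0.3 | 3.5 points | 7.6% |

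These lie towards the upper end for each r. Any randomness in accepting shrinks the 0.444. The formula for 26.13 also contains the squared difference between means, so it can exceed the SD at a single visit.

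**5. Which analysis is exposed.** Let selection shift the level by δ at both visits. In the group-by-time contrast the shift is δ − δ = 0. In a comparison at either visit it remains δ. Section 9.3 plans comparisons at each visit. If selection also affects speed of recovery, the shift is not stable and does not cancel fully. The first visit is no baseline: it follows training, and 10.4 expects a benefit already at cast removal.

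**6. What the covariates cover.** Age, imagery ability (VMIQ at one week), fracture type, occupation and sport can be fixed before training. Use of the casted hand may itself respond to training. None of the six records willingness, early pain or early function, and none is named in 9.3.

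**The case against.** The design is deliberate. Controls who knew about imagery might practise it, and 7.2 regards that bias as undetectable and potentially severe. The sponsor traded one bias for another. That reason stands, but the protocol does not discuss the selection that the trade creates.

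The plan is also not blind to confounding. It intends six covariates, measures imagery ability before training in both arms, and seeks balance on fracture type. Section 7.6 follows patients who stop treatment, so an as-allocated analysis of enrolled patients is within reach. All this stands, with the limits shown in the working.

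The information letters are not in the documents. That the experimental letter mentions the daily training time, or that the control letter is neutral, can only be inferred. The acceptance gap is stated whatever its cause.

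A reader might infer that allocation must move to after consent, with a common letter. The documents do not support that as a requirement. If those who accept the experimental letter are a subset of those who accept the control letter (assumption), 35/62 = 56% of consenters would take up training. The 5.3-point target would dilute to 5.3 × 35/62 = 3.0 points, and the sample would grow by (62/35)² = 3.1, from 52 to about 163. Changing mid-trial would also mix two consent processes.

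**Conclusion.** The point holds. Consent differs by arm, topping up corrects only the numbers, and the analysed groups are not protected by randomisation against that difference. The intention-to-treat label in 9.3 needs qualifying, and the planned covariates reduce the problem only in part.

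The size and direction of any bias cannot be derived from the documents. The 1.2 to 3.5 points rest on perfect threshold selection, the plan's SD and assumed correlations of 0.1 to 0.3 of unknown sign. They concern the PRWHE level at a visit.

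Two stronger readings are tempting:
- A correlation of 5.3/11.6 = 0.46 might seem to reproduce the whole target without any treatment effect. But the target was powered as a group-by-time interaction, from which a stable shift in level cancels; the two quantities are not alike.
- A reader might conclude that the result cannot be attributed to the training at all. The acceptance rates show differential selection, not a proven bias in outcome, and the illustrated type I error of 5.3% to 7.6% does not carry that conclusion. The documents support a limit on the causal claim.

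**What to change.** - **(a)** In 9.3, replace the unqualified intention-to-treat label with 'consenting, VMIQ-eligible patients analysed as allocated'. State that the comparison is not protected by randomisation against differential consent, and limit the conclusions accordingly.
- **(b)** Report by arm the numbers allocated, accepting and declining, with age and fracture type of accepters and decliners from the diagnosis list, where the METC permits.
- **(c)** Name the pre-training covariates from 7.1.3 in the 9.3 model: age, VMIQ, fracture type, occupation and sport. Keep use of the casted hand out of that set.
- **(d)** For further patients, collect the pain VAS and PRWHE at the existing one-week visit, before any imagery instruction. Use them in a baseline comparison and in a supportive adjusted analysis of the patients who have them.

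Items (a) and (c) cost protocol wording; (b) costs a tabulation and the committee's agreement. Item (d) costs about 4 to 5 minutes per patient. Its score is taken in a cast and after the arm-specific letter, adjusts only partly, and is missing for patients already enrolled, so it should not carry the primary comparison. Allocation after consent with a common letter remains an option for the sponsor to weigh.

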7.3 Study procedures

The study coordinator checks the diagnose lists of the department of Traumatology and Orthopedics, and identifies the female DRF-patients in the age of 45-75 years of age, who are conservatively treated. These patients will be randomly allocated to the experimental or control group. They receive an information letter and are asked to participate. When they decide to participate, they return an informed consent. When the patients visit the hospital for a medical check one week after initial treatment, the patients who are willing to participate are asked to fill out the Vividness of Motor Imagery Questionnaire. A score of 72 point or less on the internal scale (first person perspective) of the VMIQ, is one of the inclusion criteria. Therefore, this questionnaire is filled out before inclusion. The score on the VMIQ determines whether the patient can participate in the study or not. The patients who are allocated to the experimental group will receive information and instructions about the motor imagery training. To promote the imagery, the instructions are task-related:

- Flexion and extension: Patients are asked to imagine making a fist and imagine that they are slowly knocking on the table with their knuckles, making an exaggerated large movement.
- Adduction and abduction: Patients are asked to imagine that there are two dots drawn horizontally on the table in front of them. The hand lies between those dots, but there is still space between the hand and the dots. They are asked to imagine that they are trying to touch the right and the left dot with their little finger and thumb repeatedly, by only moving the palm of their hand.
- Pronation and supination: Patients are asked to imagine that they turn a key back and forth, by only using their hand and forearm.

In addition to these task-related instructions, the movements that have to be imagined are demonstrated by the study coordinator. Next, the patients are asked to repeat that movement once with their uninjured hand. The patients receive a letter that contains the instructions and are asked to repeat this protocol unsupervised at home. To promote their adherence to the motor imagery training, the patients in the experimental group will be contacted by phone on a weekly basis. To control for bias as a consequence of this extra attention, also the patients in the control group will be contacted by phone weekly.

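### Patients are allocated after a screen on sex, age and conservative treatment only, with no concealment described, so some exclusion criteria can be judged with the arm known

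*Combined protocol and SAP*

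**What the plan says.** Section 7.2 places allocation early: "Potential participants are randomly allocated to the experimental or control group before the start of the study, i.e. before inclusion". The mechanism is in the same section: "Subject numbers are randomly allocated to the experimental or the control group", using PASW, and "The order in which the patients receive their initial treatment determines their subject number". It also states "There is no blinding of the patients, nor the researcher is blinded". The section gives a reason for early allocation: controls should not learn about motor imagery, so the two arms get different letters.

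Section 7.3 gives the order of work. The study coordinator goes through the diagnosis lists and "identifies the female DRF-patients in the age of 45-75 years of age, who are conservatively treated". The next step is "These patients will be randomly allocated to the experimental or control group". The letter, consent and the one-week check follow. The VMIQ is completed at that check, and "The score on the VMIQ determines whether the patient can participate in the study or not". Section 10.2 agrees: "The outcome of this test determines the final inclusion or exclusion of the patient".

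Section 4.3 lists six exclusions: the VMIQ score, fracture pattern, complications expected to worsen function, high-energy trauma, earlier upper-limb disorders, and language.

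**The concern.** Random allocation protects the comparison only if the decision to keep a patient does not depend on the arm. Here the arm is fixed first and final inclusion comes about a week later. Nothing in the plan keeps the arm from those who apply the exclusions in between. One exclusion, complications, is defined by expected functional outcome and calls for judgement.

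If a few patients with a poor outlook are set aside more readily in one arm, the arms differ before any effect of training. The planned analysis can repair this only in part. The covariates in 7.1.3 include age, imagery ability and fracture type, but not complications or earlier disorders. Intention to treat (9.3) cannot recover patients removed before inclusion. The Summary describes a post-test-only design, so there is no pre-treatment PRWHE to adjust for.

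**Working it through.** **When each exclusion in 4.3 is applied**

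| Exclusion | What the plan says on timing | Assessor named |
|---|---|---|
| VMIQ score | Explicitly after allocation and consent (7.3, 10.2) | Completed by the patient; numeric cut-off |
| Fracture pattern | Allocation balances intra- against extra-articular (7.2), so type appears known by then | No |
| High-energy trauma | A low-energy fall is an inclusion criterion (4.2), and letters go to those meeting the inclusion criteria (10.2), so apparently before the letter; not shown to be before allocation | No |
| Complications | Not stated | No |
| Earlier upper-limb disorders | Not stated | No |
| Dutch language | Not stated | No |

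One exclusion is therefore explicitly late, two appear to be handled early, and three have no stated time. None is named in the pre-allocation screen of 7.3.

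**Inputs for size**

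- SD 26.13 PRWHE points and a target of 5 points extra decrease (4.4).
- Total N = 52 (4.4), so 52/2 = 26 per arm with equal groups.
- The plan's N reproduces. With f = 0.20, 2 measurements, and assumed defaults of correlation 0.5 and epsilon 1, λ = 0.20² × 52 × 2 / (1 − 0.5) = 8.32 on 1 and 50 df, giving power 0.807 (N = 50 gives 0.791). The point here does not depend on this.

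**Upper bound at one visit**

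Take 26 + k patients in one arm with normally distributed scores and remove the k worst. The mean of those left is −k × (mean of the k highest scores) / 26 in SD units. Simulated means of the highest scores are about 2.00, 1.80 and 1.66 SD.

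| k removed | Shift, SD | × 26.13 | If judgement correlates 0.5 with outcome (assumption) |
|---|---|---|---|
| 1 of 27 | 2.00/26 = 0.077 | 2.0 | 1.0 |
| 2 of 28 | 2 × 1.80/26 = 0.138 | 3.6 | 1.8 |
| 3 of 29 | 3 × 1.66/26 = 0.192 | 5.0 | 2.5 |

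At a correlation of 0.3 the shifts are 0.6, 1.1 and 1.5 points.

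**Change from T1 to T2**

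Patients with a poor outlook tend to score badly at both visits. With equal SDs and selection purely on T2, the shift in change is (1 − ρ) times the single-visit shift. At an assumed ρ = 0.5 this gives 1.0, 1.8 and 2.5 points even with perfect foresight. If the judgement predicts both visits equally well, the shift in change is zero.

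**Visibility**

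At the response rates in 7.2 (35% and 62%), 26 per arm needs 26/0.35 ≈ 74 and 26/0.62 ≈ 42 invitations, about 116 in all. About 116 − 52 = 64 allocated patients would leave by refusal alone. A few further exclusions would not stand out unless they are logged separately.

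**The case against.** The case on the other side is substantial, and much of it stands.

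- **Who decides.** A reader might infer that the plan has the coordinator decide eligibility with the arm known. No sentence says so. The coordinator identifies patients from the lists, and the final decider is not named.
- **How many criteria come late.** A reader might infer that most exclusions follow allocation. Only the VMIQ is explicitly placed there. It is completed by the patient and has a cut-off, which leaves little discretion. A score of exactly 72 is excluded in 4.1 and 4.3 but included in 7.3 and 10.2. Those passages must be reconciled, as a separate matter.
- **Numbering.** Giving numbers by treatment order is partly a safeguard, since it removes choice over which number a patient gets. What remains is the choice to exclude.
- **Feasibility.** It would be wrong to assume that everything except the VMIQ can be judged before allocation. Letters go out within 48 hours (10.2), and a complication may appear later. The plan does not say whether language or earlier disorders are on the diagnosis lists.
- **Size.** Setting 5.0 beside the 5-point target invites the reading that three exclusions could create the whole effect. The first figure assumes perfect foresight in one arm at one visit. The second is an extra change. The SD formula in 4.4 also contains a between-mean term, so 26.13 may exceed a single-visit SD.

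These points do not close the gap. The letter rule in 10.2 cannot mean full eligibility, because 7.3 treats the VMIQ as an inclusion criterion and applies it a week later; 10.2 also describes these patients as already allocated. The wish to keep controls uninformed explains early allocation, but it does not require whoever applies the record-based exclusions to know the arm.

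**Conclusion.** The concern holds in this form: followed as written, the plan allows at least three exclusions, one of them directly prognostic, to be judged with the arm known, and it describes no concealment. This is a route to bias in the procedure. The documents do not show that it was used. That a sequence is drawn in advance is the natural reading of 7.2, although the section does not use the word list.

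The single-visit shift is at most about 2.0, 3.6 or 5.0 PRWHE points for 1, 2 or 3 patients. It is about 1.0, 1.8 or 2.5 if judged prognosis correlates 0.5 with outcome. These figures rest on normal scores, SD 26.13, 26 patients remaining, and exclusion in one arm only. They bear on the group differences that 9.3 tests at each measurement time. For the group-by-time interaction behind the sample size, the effect would be smaller. The planned covariates may absorb part of any imbalance in what they measure, but not all of it. No change to N follows.

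**What to change.** **Patients not yet allocated.** In 7.3, apply every criterion in 4.2 and 4.3 that can be known from the record, and log the patient as eligible to invite, with the date, before the arm is looked up. Have someone other than the coordinator, for example the principal investigator, hold the PASW sequence and release the arm for each logged patient. State who applies the remaining criteria and when.

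**All patients**, including those recruited in the 2.5 years that 7.2 reports: list every post-allocation exclusion by arm, criterion and date, including VMIQ exclusions and complications found later. For patients already allocated, this reporting is the only part that can still help.

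**Cost.** A small logging and hand-over step. The different letters, allocation before consent, visits, treatment and sample size all stay as they are. Whether the principal investigator is available for each release is for the sponsor to confirm.
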